Exclusion criteria. Patients with another disease or systemic condition in addition to ALL. Presence of oral infections such as candidiasis, herpetic gingivostomatitis, reactive oral lesions. Children with Down syndrome, patients allergic to zinc or mannitol.

Elimination criteria: Patients who present with hypersensitivity to zinc or placebo (mannitol), those who develop a systemic condition that modifies their treatment or prevents oral care, as well as patients requesting to leave the study.

Definition of the variables

INTERVENTION VARIABLE				
	CONCEPTUAL DEFINITION	OPERATIONAL DEFINITION	TYPE	MEASUREMENT
ZINC	Trace element found in most of the body's cells, having catalytic, structural and cellular regulation functions.	Food supplement based on zinc sulfate in doses of 50-100 mg / day for prevention and treatment of oropharyngeal mucositis .	Qualitative Nominal	1. Apply 2. No apply

DEPENDENT VARIABLES				
ORAL HYGIENE	Combination of physical and chemical measures to control the formation of bacterial plaque, which is the most important risk factor in the development and evolution of caries and periodontal disease.	Oral hygiene registered with the O'Leary index (bacterial plaque on dental surfaces identified by a developer. It is obtained from the sum of stained dental surfaces / total surfaces, multiplied by 100.	Qualitative Ordinal	1. Good 0% to 15%: 2. Regulate 16% to 49%: 3. Poor: 3.50% to 100%:
OM RECOVERY DAYS	Days in which some degree of OM is clinically observed until healing.	Number of days from the clinical diagnosis of OM (Grade ≥ 1) to recovery of the oral epithelium.	Continuous	1,2 ,3 4, 5...

INDEPENDENT VARIABLES

ORAL MUCOSITIS	Inflammatory reaction that affects the entire gastrointestinal tract from the mouth to the anus caused by chemo and / or radiotherapy.	Inflammatory reaction of the oropharyngeal mucosa to chemotherapeutic drugs, according to the WHO scale.	Qualitative Ordinal	Grade 0. Healthy Grade 1. Erythema Grade 2. Ulcers Grade 3. Extensive ulcers Grade 4. Ulcers and necrosis.
PAIN	Localized and subjective sensory perception that is the result of an excitation or stimulation of specialized sensory nerve endings.	Visual scale of facial expressions	Qualitative Ordinal	0-2 No pain 3-4 Mild 5-6 Moderate 7-8 Intense 9-10 Maximum

SOCIODEMOGRAPHICAL VARIABLES

	CONCEPTUAL DEFINITION	OPERATIONAL DEFINITION	TYPE	MEASUREMENT

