AGE	Life time elapsed from birth to the current date.	Life time in years recorded in the clinical record.	Quantitative Discreet	Years 0 a 18
SEX	Physiological and sexual characteristics with which men and women are born.	Biological characteristics recorded in the clinical file as female and male.	Qualitative Nominal Dichotomous	1. Female 2. Male

CONFUSORY VARIABLES				
ACUTE LEUKEMIA LYMPHOBLASTICS (LAL)	Neoplastic disease that results from a clonal proliferation of lymphoid precursors (lymphoblasts), which infiltrates bone marrow, produces a variable degree of pancytopenia and can compromise different organs and / or systems.	Type of leukemia recorded in the clinical file according to the immunophenotype.	Qualitative Nominal	1. Pro B leukemia 2. Common leukemia 3. Pre-B leukemia 4. Mature leukemia B 5. T leukemia (precursors) 6. T leukemia (mature)
NEUTROPENIA	Reduction of peripheral blood neutrophil count .	Absolute neutrophil count obtained by laboratory test (blood count).	Qualitative Ordinal	0. Absence of neutropenia 1. Mild: 1,000-1,500 / ml 2. Moderate: 500-1,000 / ml 3. Severe: <500 / ml
OPPORTUNIST INFECTIONS	Infections in immunosuppressed patients, whether of bacterial, fungal or viral origin.	Record of suggestive lesions by C. albicans and determination by means of KOH, suggestive lesions of herpes and determination by PCR, suggestive bacterial lesions and detection through cultures.	Qualitative Nominal	0. Absent 1. Fungal 2. Bacterial 3. Viral

STUDY DESIGN

Double blind clinical trial

Sampling: Sequential non-probabilistic until the required number of participants is completed.

Randomization: sealed envelopes for group assignment.

Sample size calculation

Formula for the difference of proportions (incidence of OM).

$$\frac{[Z_{\alpha} \sqrt{2\pi_1(1-\pi_1)} - Z_{\beta} \sqrt{2\pi_1(1-\pi_1) + 2\pi_2(1-\pi_2)}]^2}{(\pi_1 - \pi_2)^2}$$

Assumptions:

$$\alpha = 0.05$$

$$\text{Power} = 0.90$$

Rambod study findings: The effect of zinc sulfate on prevention, incidence, and severity of OM in leukemia patients undergoing chemotherapy.

$$Z_{\alpha} = 1.96$$

$$Z_{\beta} = -0.84$$

$$n = 86$$

$$\pi_1 = 75\%$$

$$\pi_2 = 47\%$$

$$\pi_1 - \pi_2 = 28\%$$

$$\frac{[1.96 \sqrt{2(0.75)(0.25)} - (-0.84) \sqrt{(0.75)(0.25) + 2(0.47)(0.53)}]^2}{(0.75 - 0.47)^2} = 46$$

41/5000

15% losses = 53 patients per group

Statistical Analysis Plan

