Descriptive statistics will be used to characterize the population using measures of central tendency and dispersion for continuous variables and distributions of relative and absolute frequencies for categorical variables. Independent t-test and Chi-square test for the difference between the two study groups. Analysis of variance (ANOVA) to compare the two groups with respect to the OM in the five time periods.

METHODOLOGY

Randomization

The randomization will be taught by [name] [name], assigned to the Oncology service, who is unaware of the objective of the study.

The randomization technique will be carried out through sealed envelopes, which will indicate the bottle that will correspond to the patient, identified as treatment "A" and "B". Likewise, to ensure that the groups are balanced, blocks of 6 sealed envelopes containing 3 patients will be made for each group.

Blinding

The patient and the investigator will be blinded; for this, the 50 mg zinc and placebo tablets will be similar in size, color, shape, weight and taste; the bottles will be classified into codes A and B, which in turn will have the same shape, size and color. All of the above will be done through the Pharmaceuticals GREMAR S.A. de C.V., which is a Mexican company that has a line of food supplements located in Mexico City.

An independent investigator (who will be blinded for the purpose of the study) will be requested to receive the medications (zinc / placebo) prepared by the Pharmaceuticals GREMAR S.A. of C.V., so that it provides to the principal investigator only the bottles coded as "A" and "B". At the end of the intervention, the independent investigator will be asked to reveal the coding of the medications to determine which group (Group 1 placebo or Group 2 zinc) corresponds to treatment A and B respectively.

Instruments

WHO OM scale

The oral mucositis scale proposed by the World Health Organization (WHO) in 1979 will be used. This instrument was designed based on objective signs (erythema or ulcer) and subjective signs (mucosal sensitivity, ability to swallow).

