Six randomized patients with a recent diagnosis of childhood cancer who start chemotherapy will be selected, data from the clinical record will be obtained to determine if it meets the inclusion criteria. The patient identified as eligible will be visited at his place of hospitalization or in the outpatient office of the Oncology Service.

The intervention will be assigned under the balanced block scheme. Children will be randomly assigned to each of the two treatment groups using sealed envelopes.

The sequence of procedures and the complete description of the instruments can be found in the Annex "Pilot test applicator manual".

[figure not shown]
Information collection method

A data record sheet will be filled out that includes the patient's identification form (name, age, sex), type of ALL, chemotherapy phase and blood count; which will be obtained from the clinical file. It will also include the table for the determination of the WHO OM scale, the oral hygiene index and the opportunistic infection registry.

Registration and processing method.

[figure not shown]
The data will be recorded in an Epidata database and analyzed using the STATA 14 statistical program.

FLOWCHART 1

In the previous study by Rambod et al. (12), a difference in the incidence of OM of 28% was obtained and from this, for the present study the estimated sample size was 106 subjects.

Complying with one of the principles that govern clinical trials, which is to reduce the risk of the operated subjects to the minimum possible, in case of observing adverse reactions the suspension of the study will be indicated; while if there are no complications, recruitment will continue until a sample size of 53 subjects is met and at this point the intermediate analysis will be performed as shown in Flowchart 2.

ETHICAL CONSIDERATIONS

In accordance with the principles and guidelines established by good clinical practices (BPC), in accordance with the principles set forth in the Helsinki Declaration of 1964 and with the support provided in the General Health Law, in the Regulations of the General Health Law in the area of provision of Health Care Services, which establishes that the individual welfare of the subjects must sometimes prevail in a study, over the interests of science and the community.

This study will be carried out with the strict observation of the recognized scientific principles and respect, handling the affected data anonymously and confidentially.

Consent

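### The 15% loss allowance is added to 46 rather than divided out, so 53 per group leaves 45 evaluable children at the plan's own loss rate

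*Combined protocol and SAP*

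**What the plan says.** Under Study design, Sample size calculation, the protocol takes an oral mucositis incidence of 75% in the control group and 47% in the zinc group and obtains 46 per group. The loss allowance follows in a single line, with no formula shown: "15% losses = 53 patients per group".

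The text after Flowchart 1 doubles this: "for the present study the estimated sample size was 106 subjects". It also sets the intermediate analysis at 53 subjects, which is half of that total. Allocation is equal, since the Randomization section gives "blocks of 6 sealed envelopes containing 3 patients will be made for each group".

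The elimination criteria show who may be lost. Besides children with hypersensitivity to either product, they name "those who develop a systemic condition that modifies their treatment or prevents oral care, as well as patients requesting to leave the study". These are children who leave or are removed after entry. No other section redefines the 15% or adds further children.

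**The concern.** A loss allowance is meant to ensure that, after the expected share of enrolled children has gone, the required number is left. That calls for dividing the required number by the proportion retained. Multiplying by one plus the loss rate always gives too few, because it takes the percentage of the smaller, required number and not of the larger, enrolled number.

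The figure of 53 looks like the product of that shortcut. If so, the number the trial recruits to does not provide the protection its own line describes, and a reader told that 15% losses are covered is misinformed. The same rule would also understate any corrected sample size, since the gap widens as the base number grows.

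**Working it through.** **Inputs, all from Sample size calculation:** incidences 0.75 and 0.47; z for alpha 1.96; z for power 0.84 in absolute value; 46 per group before losses; losses 15%; 53 per group after losses.

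**1. Reproduce the 46.** The expression with the protocol's numbers substituted is

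[1.96 × √(2 × 0.75 × 0.25) + 0.84 × √(0.75 × 0.25 + 2 × 0.47 × 0.53)]² / 0.28²
= (1.2002 + 0.6956)² / 0.0784 = 45.84, rounded up to 46.

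The stated figure is reproduced.

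**2. Reproduce the 53.**

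| Rule | From 46 | From unrounded 45.84 |
|---|---|---|
| n × (1 + 0.15) | 52.9 → 53 | 52.7 → 53 |
| n / (1 − 0.15) | 54.12 → 55 | 53.93 → 54 |

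Only multiplication gives 53. Division, rounded up, does not give it from either base.

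**3. Apply the plan's loss rate to 53.**

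- 53 × 0.85 = 45.05 per group, or 106 × 0.85 = 90.1 in total, against 46 and 92 required.
- In whole children, 7 losses are 7/53 = 13.2% and leave 46; 8 losses are 8/53 = 15.1% and leave 45.
- For comparison, 55 × 0.85 = 46.75, which is enough. 54 × 0.85 = 45.9, which just misses 46.

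**4. Cost in power.** At 75% against 47%, two-sided 5%, equal groups:

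| Evaluable per group | Exact power, uncorrected chi-square test | Normal approximation |
|---|---|---|
| 45 | 78.9% | 78.7% |
| 46 | 79.0% | 79.6% |

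The loss is between 0.2 and 0.9 of a percentage point, depending on the method.

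**5. Does the error survive a change of base?** Yes. With the quantile for 90% power, the standard two-proportion formula gives 62 per group. Multiplying gives 62 × 1.15 = 71.3, so 72; dividing gives 62 / 0.85 = 72.9, so 73.

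**The case against.** Four points can be made for the plan.

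*The factor of 1.15 is inferred.* This is true, because the protocol does not show the step. But the finding does not depend on how 53 was reached: losing 15% of 53 leaves 45 whatever the method.

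*Adding 15% of the base is a common shorthand, and the protocol does not say what the 15% is a percentage of.* Read that way, the arithmetic is right and the label is wrong. The line speaks of losses, and the elimination criteria describe children who drop out after entry, so the natural denominator is the number enrolled.

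*The consequence is negligible.* This stands. The shortfall is one evaluable child per group, at a loss rate for which the protocol gives no source. The enrolment gap is 2 per group from the rounded 46, or 1 per group from the unrounded 45.84. No design decision turns on it, and there is no evident harm to the intermediate analysis.

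*The base of 46 has larger faults.* This also stands. Power is declared as 0.90 while the quantile 0.84 belongs to 80%, and the substituted expression drops a factor of 2 that the printed formula contains (as printed, it gives 50.3, so 51). These are separate errors and do not remove this one. They are, however, a good reason not to replace 106 with a new total built on 46.

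**Conclusion.** The concern holds, as a minor error in a stated figure. From the plan's own 46 and its own 15%, 53 per group leaves 45 evaluable children, not 46. Covering 15% would take 55 per group (110 in total), so the stated numbers are short by 2 per group and 4 in total. What 53 does cover is losses of up to 13%. The power cost is under one percentage point.

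This rests on two readings: that 46 is the number wanted for analysis, and that the 15% refers to children enrolled. Both are the ordinary sense of the line, and nothing in the document points elsewhere. It does not rest on 46 itself being adequate, which is a separate and more serious question.

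**What to change.** Restate the loss line so that it matches the numbers, for example: 53 per group allows for about 13% losses (46 evaluable); with 15% losses, 45 per group would remain. This changes one line, enrols no additional children and leaves 106 as it is. The only cost is a slightly less favourable stated allowance. The 13% describes what 53 can absorb and should not be presented as a forecast of losses.

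In any recalculation, divide the required number by one minus the loss rate and show the step. A revised enrolment total should wait until the power quantile and the formula behind the 46 have been corrected. Moving to 55 per group now would give a new figure that still does not follow from the declared power.

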The most frequent oral complications that have been reported in pediatric patients under chemotherapy are oropharyngeal mucositis (OM), xerostomia, caries and gingivitis, followed by opportunistic infections, which occur in up to 30% of cases; being more frequent those of fungal origin, although they can also be of bacterial or viral origin (candidiasis, cold sores, aphthous stomatitis and angular cheilitis). In the Mexican population, study by Castellanos et al., On oral lesions in children with acute lymphoblastic leukemia of the National Institute of Pediatrics, found that during the first 8 weeks of onset of chemotherapy, 71% of children developed some oral lesion the most frequent being OM (65%); which in severe grades (III or IV) was associated with neutropenia and malnutrition.⁶

Oral Mucositis

Oropharyngeal mucositis (OM) is a lesion of the oral and oropharyngeal mucosa that appears as a result of inflammatory changes in epithelial and subepithelial cells caused by the cytotoxic effects of chemo or radiotherapy.¹¹

The OM consists of four phases: 1) initial inflammation, 2) vascular and epithelial rupture 3) ulcerative / bacteriological and 4) healing. (7) It begins 3 to 10 days after the start of chemotherapy and may persist for 3 weeks. It reaches its maximum peak around 7 to 14 days and subsequently resolves slowly unless it is complicated by an infection; while, better resolution has been associated with neutrophil recovery.¹²⁻¹⁴

OM occurs at any age; however, it has been observed that the prevalence is higher in pediatric patients than in adults, which can be explained by the higher rate of cellular replication during childhood. It is estimated that 52 to 80% of children undergoing chemotherapy will experience some degree of OM, which varies according to the type of cancer and antineoplastic treatment. In general, children with hematologic malignancies present more frequently with OM than those with solid tumors.¹⁴

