Chemotherapeutic agents are not equally stomatotoxic.¹⁵ The extent of damage depends on the drug used, the duration of treatment, the dose and the route of administration; Therefore, bolus infusion, prolonged or repeated administration, compared with low doses of chemotherapy are associated with an increased risk of developing OM. Drugs that affect DNA synthesis, such as antimetabolites (methotrexate, 5-fluorouracil) and purine analogues (cytarabine), have been shown to cause OM from 40-60%. Etoposide, cyclophosphamide, doxorubicin, daunorubicin, docetaxel and paclitaxel have also been related.¹³

In the ulcerative phase of OM there are complications such as pain, difficulty eating, swallowing and speaking, which may require the use of analgesics and nutritional support.¹² The most severe grades are related to complications such as: deterioration in quality of life, increase in the duration and cost of hospital stay, decrease in the survival rate of patients due to delayed treatment or reduction in the dose of chemotherapy, as well as a higher incidence of secondary infections and may even lead to sepsis and death.¹⁶

Dental care in pediatric patients with cancer is essential, preventive measures and specific intervention actions are required to improve oral conditions that favor good nutrition and reduce the risk of infections.¹⁶

Recent research has found that OM is the result of a complex process that begins in the submucosal endothelium and fibroblasts, with the influence of local cytokines and not just direct epithelial cell damage. Thus, through a better understanding of the common intracellular pathway of the endothelium, cell apoptosis and interactions between apoptotic and inflammatory pathways, new treatments have been developed, which although some have been used in the pediatric population, none have been accepted as the treatment of choice.¹⁴

There are various treatments for OM including medications such as amifostine, palifermin, benzydamine, HCl and pentoxifylline, low intensity laser therapy and various organic products such as zinc; however, the effects of these interventions have not been fully confirmed.¹²

Zinc

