Gholizadeh et al. ⁽³⁸⁾ (2017)	Chemotherapy	220 mg capsules equivalent to 50 mg of zinc sulfate 3 times / day 150 mg / day VS. Placebo	Myeloid and lymphoid leukemia 18 - 71 years old	Randomized clinical trial n = 140 4 weeks follow-up (week 2 and 4)	Reduction of severity of OM grade 3-4 p = 0.004
Rambod et al. ⁽¹²⁾ (2018)	Chemotherapy	220 mg capsules equivalent to 50 mg of zinc sulfate 3 times / day 150 mg / day VS. Placebo	Myeloid and lymphoid leukemia > 18 years	Randomized triple blind clinical trial n = 86 14 days WHO oral mucositis scale Oral Mucositis Index	OM prevention p = 0.01 OM severity reduction p = 0.01

OM; Oral Mucositis, HDC: High doses of chemotherapy, HPCT: hematopoietic progenitor cell transplantation.

There are currently no studies evaluating the effectiveness of zinc for the prevention of OM in pediatric patients receiving chemotherapy, so the purpose of this study is to conduct a clinical trial that evaluated the impact of the use of zinc for the prevention of OM in children with LAL in chemotherapy.

PROBLEM STATEMENT

The development of OM in patients with acute leukemia varies between 81.3% and 90% .8 The available literature recognizes the importance of prevention and treatment of OM, since it has an impact on the quality of life and even on the prognosis of disease in patients under chemotherapy. The better understanding of the pathophysiology of this entity has allowed the development of new therapies, among which the use of zinc, which has shown beneficial effects in the prevention of OM in adult patients with leukemia, and because they are not counted with studies in pediatric patients with ALL; The following research question arises:

What is the impact of the use of zinc for the prevention, incidence and reduction of the severity of oropharyngeal mucositis in patients with acute lymphoblastic leukemia in chemotherapy during the period from 2019 to 2020?

JUSTIFICATION

In the National Institute of Pediatrics, about 100 new cases of ALL enter each year, which will require a multidisciplinary approach throughout the course of cancer treatment, which includes the participation of the stomatologist, who must continually establish preventive and therapeutic measures of complications buccal, among which the OM stands out as a reason for frequent consultation.

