Cancer patients will experience pain, limitation and psychological involvement due to oral OM; this debilitating condition also significantly affects nutritional intake, oral care and quality of life, representing up to 21.9% of the reasons for hospitalization.8 OM, if not properly treated or associated with prolonged neutropenia, may end in septic shock and even the death of the patient.

The use of zinc has been studied as a low-cost alternative for OM, so the realization of this study will determine the effectiveness of the use of zinc for the prevention and reduction of complications due to OM in pediatric patients with ALL of the Institute National Pediatrics.

OBJECTIVE

To assess the impact of the use of zinc in the prevention, incidence and severity of oropharyngeal mucositis in patients with acute lymphoblastic leukemia in chemotherapy (induction and consolidation phase) of the National Institute of Pediatrics and the Children's Hospital of Mexico during the period from 2019 to 2020.

SPECIFIC OBJECTIVES

1. Determine the incidence of OM in patients with ALL assigned control group (Group 1: oral care + placebo) versus the intervention group (Group 2: oral care + zinc).
2. Identify if there are differences in OM severity between Group 1 and Group 2.
3. Identify if there are differences in the recovery time of the OM between Group 1 and Group 2.
4. Identify if there is an association between the severity of OM and severe neutropenia in both groups.

HYPOTHESIS

The use of zinc reduces the incidence and severity of OM in pediatric patients with ALL in chemotherapy compared to the control group.

MATERIAL AND METHODS

Type of study: Randomized, double blind clinical trial.

Duration of the intervention: Induction and consolidation phase of chemotherapy (2 to 2.5 months).

Inclusion Period: from August 2019 to May 2020.

Study population

Target population: patients of both sexes from 3 to 18 years of age with newly diagnosed or relapsed ALL during the period from 2019 to 2020.

Study population: patients of both sexes from 3 to 18 years of age with recently diagnosed or relapsed ALL treated by the Pediatric Oncology service of the National Institute of Pediatrics and the Children's Hospital of Mexico during the period from 2019 to 2020.

Selection criteria

Inclusion criteria: Patients aged 3 to 18 years with a recent diagnosis of ALL or relapse who accept by informed consent to participate in the study.

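### Does leaving baseline covariates out of the mucositis comparisons undermine a trial that mixes newly diagnosed and relapsed children aged 3 to 18?

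*Combined protocol and SAP*

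**What the plan says.** The Statistical Analysis Plan section gives descriptive statistics, then "Independent t-test and Chi-square test for the difference between the two study groups", then an ANOVA of mucositis in the two groups over five time periods. No comparison names a covariate.

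Under Randomization, "blocks of 6 sealed envelopes containing 3 patients will be made for each group". No stratification factor is stated there or under Stages of the study.

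The inclusion criterion is "Patients aged 3 to 18 years with a recent diagnosis of ALL or relapse", with consent. Recruitment is at two hospitals.

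The Definition of the variables section lists leukaemia immunophenotype, neutropenia and opportunistic infections as confounders, but no test in the analysis plan uses them. Information collection method describes a record sheet with age, sex, type of leukaemia, chemotherapy phase and blood count. It names neither relapse status nor hospital, but the sheet itself is not reproduced.

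**The concern.** The population is visibly mixed, and the Background hints that the mix matters. It says of mucositis that "the prevalence is higher in pediatric patients than in adults", and that "prolonged or repeated administration, compared with low doses of chemotherapy are associated with an increased risk of developing OM". Relapsed children have usually had chemotherapy before, so one could expect relapse status and age to predict the outcome.

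If so, three things might be at stake: a chance imbalance between the groups, power given away by ignoring prognostic information, and an adjusted result added later with covariates chosen after the data were seen. A list of confounders that no analysis uses strengthens the impression of something left unfinished.

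**Working it through.** **1. The plan's own figure.** Inputs from Sample size calculation: 75% against 47%, Z values 1.96 and -0.84.

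- 1.96 × √(2 × 0.75 × 0.25) = 1.200
- 0.84 × √(0.75 × 0.25 + 2 × 0.47 × 0.53) = 0.696
- (1.200 + 0.696)² / 0.28² = 45.8, so 46 per group, as stated
- 46 × 1.15 = 52.9, so 53 per group, as stated

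An unadjusted two-group test with 46 per group has power 79.6%. The stated power of 90% does not match a Z value of 0.84. That is a separate matter, and covariate adjustment would not repair it.

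**2. Does omitting a covariate damage the test?** Simulation with blocks of 6, one outcome per child, a common risk of 75%, and a binary covariate with prevalence 20% or 50% and odds ratio 1 to 8 (both assumed, since the documents give neither); 40,000 trials per setting. The chi-square type I error was 0.048 to 0.053 throughout. Randomisation makes the covariate independent of treatment, so chance imbalance is already part of the 5%.

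**3. How much power is at issue with one covariate?** Same simulation at 75% against 47%, comparing the chi-square with a Mantel-Haenszel test stratified on the covariate. Change in power, in points, at prevalence 20% / 50%:

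| Odds ratio | 46 per group | 53 per group |
|---|---|---|
| 1 | 0.0 / 0.0 | -0.8 / -0.8 |
| 2 | +0.5 / +1.1 | -0.2 / +0.1 |
| 4 | +2.0 / +4.2 | +1.1 / +2.7 |
| 8 | +3.8 / +8.1 | +2.3 / +6.1 |

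**4. How much with relapse status and age together?** Assumptions: 53 × 0.85 ≈ 45 evaluable per group; 20% relapsed; age uniform over 3 to 18; both factors equally prognostic; a 28-point difference kept. The control risks are 75% (sample size), 65% (Background, children at one of the two hospitals), and 81.3% and 90% (Problem Statement). The adjusted analysis is a linear regression of mucositis (yes/no) on treatment, relapse status and age with HC2 robust standard errors. Change in power, adjusted minus chi-square, in points, from 10,000 trials per setting, by joint c-statistic of the two covariates:

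| Risks | 0.50 | 0.58 | 0.63 | 0.70 | 0.73 |
|---|---|---|---|---|---|
| 75 v 47 | -1.0 | +0.4 | +1.7 | +3.9 | +5.2 |
| 65 v 37 | +0.4 | +1.3 | +2.3 | +5.8 | +7.2 |
| 81.3 v 53.3 | -1.6 | -0.9 | +0.2 | +1.8 | +3.8 |
| 90 v 62 | -1.4 | -1.1 | -0.2 | +1.2 | +1.7 |

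Repeat runs moved these by about one point; at 65% against 37% and c 0.63 one gave +2.7. Tenths of a point should not be read closely. The +0.4 for inert covariates, for example, reflects the discreteness of the chi-square at exactly 45 per group; at 46 per group it becomes -0.3.

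**5. Which column applies?** The documents do not say. The first Background statement compares children with adults, and everyone here is 3 to 18. The second concerns how chemotherapy is given and does not mention an earlier line of treatment; reading it as relapse status is inference. Neither gives a strength of association. Nothing supports the two right-hand columns over the others.

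**The case for a change.** The best case for a change does not depend on power. The plan calls some variables confounders and never says what is done with them. Two of the three, neutropenia and opportunistic infections, can arise during chemotherapy, after assignment, so an analyst taking the label at face value might adjust the treatment comparison for them. The split written into eligibility is not listed as a variable at all. A few lines naming baseline covariates before the planned interim look at 53 subjects would settle this cheaply.

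The facts in that argument stand, and prespecifying covariates is good practice when an adjusted analysis is intended. But the plan intends none. The risk it guards against is an analysis that the plan does not contain, and one added later could be recognised as unplanned. Objective 4 uses neutropenia only for its association with severity.

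The change also has costs: 1 to 2 points of power if the covariates are inert and the adjusted analysis decides (about 2.4 at the interim), a need to state which of two analyses of the same outcome decides, and reliance on a relapse field not shown to be on the record sheet. Relapse status is at least known at recruitment, from the bone marrow result.

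**Conclusion.** The concern does not hold. The plan is unadjusted and the population is mixed, but in a randomised comparison that causes neither bias nor an inflated error rate. The effect on power has no reliable sign: from -1.6 to about +2.7 points for covariates of no to modest strength, and +1.7 to +7.2 points only at a c-statistic of 0.73. Adjusting is a trade-off the investigators may take or leave.

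This rests on the assumed 20% relapsed, uniform age, equal prognostic weights and a 28-point difference. It is also narrow: it concerns covariate omission with one incidence outcome per child. It does not vouch for pooling repeated cycles as if independent, eliminating patients after randomisation, or an interim look with no stated alpha rule. Recovery days exist only for children who develop mucositis, so the randomisation argument does not carry over to them in full. Naming baseline covariates for incidence would resolve none of these.
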